### 7.2.3 Assessing for response during and after neoadjuvant cetuximab

Response to cetuximab will be assessed by RECIST criteria.

#### 7.2.3.1 Response by RECIST criteria

After 8 weeks of Cetuximab has been completed, the patient will have a restaging CT scan with IV contrast for comparison to the first CT scan performed prior to neoadjuvant cetuximab. CT response will be evaluated using RECIST criteria for partial response versus progressive or stable disease ( Eisenhauer et al. 2009). The RECIST criteria will be applied to the combination of primary site and associated neck lymphadenopathy.

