## 6. Study Parameters

Evaluations	Pre-cetuximab	Weekly during neoadjuvant cetuximab	Post-cetuximab (Week 9)	At surgery or prior to RT 	30 days after surgery or XRT	Follow ups every 3 months after surgery or XRT for 2 years	After locoregional or distant failure
History, physical exam and tumor site assessment	X  (within 14 days of treatment)	X 	X 		X 	X 	X 
Photo of tumor and/or rash at head, neck, upper torso put into EMR	X (within 14 days of treatment)	X 	X 				
Incisional/core biopsy of primary tumor and loco-regional lymph nodes if involved	X  (within 30 days of treatment)			X  (any time during this interval)			X (within 30 days of relapse)
Biopsy of skin	X  (within 30 days of treatment)			X  (any time during this interval)			X (within 30 days of relapse)
CBC, differential, platelets	X (within 14 days of treatment)	X			X	X	
Serum Chemistries 	X (within 14 days of treatment)	X	X	X	X	X	
Liver Enzymes 	X (within 14 days of treatment)	X			X	X	
Pregnancy Test 	X (within 14 days of treatment)						

Radiographic Assessments 	X  (within 30 days of treatment)		X 			X	X 
---------------------------------------	---	--	----------------	--	--	---	----------------

\*A +/- 2 day window is allowed for all study assessments indicated on this trial except treatment for which a +/- 1 day window is allowed.

1. To include toxicity assessment, ECOG performance status, weight
2. Includes: Electrolytes, including serum magnesium, potassium, Calcium, BUN, Creatinine, Glucose,
3. Includes: Total and Direct. Bilirubin, AST/ALT, Alkaline Phosphatase, Albumin, Total Protein.
4. Women 18-55 who have not undergone menopause must have urine pregnancy test within 14 days of enrollment.
5. Tumor assessments as indicated by investigator, i.e. PET/CT, CT neck, chest/abdomen and pelvis or MRI of neck as needed to be obtained no more than 1 month prior to cetuximab; then per standard of care, in general, every three months after conclusion of surgery or XRT.
6. Every 7 days
7. Includes evaluation by surgery and radiation oncology for optimal local therapy. Surgery will assess optimal timing of rebiopsy during their evaluation of patient once neoadjuvant therapy is complete.
8. See section 11

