#### 7.2.2 Neoadjuvant Cetuximab

Patients who agree and are eligible for this protocol will initially receive 8 weeks of neoadjuvant cetuximab. The initial dose of cetuximab will be  $400 \text{ mg/m}^2 \text{ IV}$ , followed by

weekly doses of cetuximab  $250 \text{ mg/m}^2$  IV to complete 8 total weeks of treatment. Even if a patient is found to have a cetuximab related folliculitis, they will complete the scheduled 8 weeks of neoadjuvant cetuximab.

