Grade 1: Transient flushing or rash; drug fever < 38° C (< 100° F)	For mild infusion reactions manifesting only as delayed drug fever, consider administering prophylactic antihistamine medications for subsequent doses. Maintain the cetuximab dose, but slow the infusion rate by 50%. Acetaminophen or a non-steroidal anti-inflammatory drug (NSAID) may be administered prior to subsequent cetuximab infusions, if not otherwise contraindicated in subjects.

Grade 2: Rash; flushing; urticaria; dyspnea; drug fever $\geq 38$ C ( $\geq 100$ ° F)	For moderate infusion reactions manifesting only as delayed drug fever, slow the infusion rate for cetuximab by 50% and consider administering antihistamine medications and/or steroid medications. Maintain the cetuximab dose. Acetaminophen or a non-steroidal anti-inflammatory drug (NSAID) may be administered prior to subsequent cetuximab infusions, if not otherwise contraindicated in subjects.
Grade 3: Symptomatic bronchospasm with or without urticaria; parenteral medication(s) indicated; allergy related edema/angioedema; hypotension	Severe infusion reactions require immediate interruption of cetuximab infusion and permanent discontinuation from further treatment with cetuximab. Appropriate medical therapy including epinephrine, corticosteroids, diphenhydramine, bronchodilators, and oxygen should be available for use in the treatment of such reactions. Subjects should be carefully observed until the complete resolution of all signs and symptoms.
Grade 4: Anaphylaxis	NO FURTHER STUDY DRUG THERAPY. Life threatening infusion reactions require immediate interruption of cetuximab infusion and permanent discontinuation from further treatment with cetuximab. Appropriate medical therapy including epinephrine, corticosteroids, diphenhydramine, bronchodilators, and oxygen should be available for use in the treatment of such reactions. Subjects should be carefully observed until the complete resolution of all signs and symptoms.

**7.3.3.3 Rash:** Dermatologic toxicities, including acneiform rash, skin drying and fissuring, paronychial inflammation, infectious sequelae (for example *S. aureus* sepsis, abscess formation, cellulitis, blepharitis, conjunctivitis, keratitis, cheilitis), and hypertrichosis occurred in patients receiving Cetuximab therapy. Acneiform rash occurred in 76–88% of 1373 patients receiving Cetuximab in clinical trials. Severe acneiform rash occurred in 1–17% of patients.

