Nail Ridging	Asymptomatic; clinical or diagnostic observations only; intervention not indicated	—	—	—

Cetuximab dose should be modified per the following table in case of severe (grade 3/4) rash:

Occurrence of Severe (Grade3/4) acneiform	Cetuximab modification
---	------------------------

rash	
1 st Occurrence	Delay infusion 1 to 2 weeks. If there is improvement, continue cetuximab at at 250 mg/m  . If there is no improvement, discontinue cetuximab.
2 nd Occurrence	Delay infusion 1 to 2 weeks. If there is improvement, continue cetuximab at at 200 mg/m  . If there is no improvement, discontinue cetuximab.
3 rd Occurrence	Delay infusion 1 to 2 weeks. If there is improvement, continue cetuximab at at 150 mg/m  . If there is no improvement, discontinue cetuximab.
4 th Occurrence	Discontinue cetuximab

For the occurrence of grade 1 or 2 rash, see supportive care guidelines in section 7.4.5.1.

**7.3.4 Dose modifications for other toxicity:** due to lack of evidence that cetuximab contributes to these toxicities, cetuximab dose will not be altered for renal failure, fatigue, nausea/vomiting.

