## **10. Removal of Patients from Study/Off Study Criteria**

In the absence of treatment delays due to adverse events, treatment may continue until one of the following criteria applies:

- a) Intercurrent illness that prevents further administration of treatment,
- b) Patient decides to withdraw from the study,
- c) Noncompliance with treatment plan,
- d) General or specific changes in the patient's condition render the patient unacceptable for further treatment in the judgment of the investigator,
- e) Protocol violation - any patient found to have entered this study in violation of the protocol might be discontinued from the study at the discretion of the Principal Investigator.

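### The response CT is ordered only after 8 completed weeks of cetuximab, and no passage expressly orders one for patients who stop early

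*Combined protocol and SAP*

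**What the plan says.** The primary outcome is the RECIST response rate (Section 15.4), tested in 20 patients. The instruction that produces it is in Section 7.2.3.1: "After 8 weeks of Cetuximab has been completed, the patient will have a restaging CT scan with IV contrast". Section 7.2.2 sets the course as weekly doses "IV to complete 8 total weeks of treatment".

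The Section 6 schedule places this imaging in the column headed "Post-cetuximab (Week 9"), and its footer adds: "A +/- 2 day window is allowed for all study assessments indicated on this trial". That column holds the only imaging between baseline and local therapy; the column for surgery or the time before RT has none. Imaging footnote 5 sets a limit for the baseline scan and continues "then per standard of care, in general, every three months after conclusion of surgery or XRT".

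The protocol foresees courses that are interrupted or stopped:

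- **Severe rash (table in 7.3.3.3).** At each of the first three occurrences: "Delay infusion 1 to 2 weeks". Drug is stopped if there is no improvement, or at the fourth occurrence.
- **Infusion reactions (7.3.3.2).** For Grade 4: "Life threatening infusion reactions require immediate interruption of cetuximab infusion and permanent discontinuation from further treatment with cetuximab".
- **Lung toxicity (7.3.4.3).** Confirmed interstitial lung disease ends treatment.
- **Other reasons.** Section 10, titled "Removal of Patients from Study/Off Study Criteria", lists intercurrent illness, withdrawal, noncompliance, change in condition and protocol violation. It asks for no exit scan.

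Section 13.2 makes off-treatment data, including best response, due within 14 days after protocol treatment ends. It sets a form deadline and does not order a scan.

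**The concern.** A patient who stops at dose 3 never meets the condition in Section 7.2.3.1. A site following that text has no order to scan before sending the patient to surgery or radiotherapy. The next scheduled imaging comes during follow-up after local therapy, when the target lesion has been removed or irradiated. An analysis rule can decide how to count such a patient, but it cannot recover the measurement.

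The loss would not be random, because the reasons for stopping are toxicity and clinical change. Section 7.3.3.1 itself cites a link between cetuximab folliculitis and benefit, so patients who stop for rash may differ in response from those who continue. The sample size in Section 15.2 has no allowance for missing responses: the 20 patients planned in Section 4.1 are the same 20 in the power calculation.

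**Working it through.** **1. Reproduce the plan's figures.** Inputs from Sections 15.1 and 15.2: n = 20, null rate 10%, expected rate 30%, one-sided exact binomial test at 0.05. With X the number of responders,

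P(X ≥ r) = 1 − Σ(k = 0 to r−1) C(n,k) p^k (1−p)^(n−k).

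- r = 4: type I error 13.3%, too large.
- r = 5: type I error 4.32%, power 76.2%. Both match Section 15.2, so the implied rule is at least 5 responders of 20.

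**2. Cost of unscanned patients.** The documents give no rate of missing scans, so 1 to 4 is an assumption. It is also assumed that being unscanned is unrelated to response. With m scanned patients and the cut-off at 5:

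| Unscanned | m | Type I error (10%) | Power (30%) |
|---|---|---|---|
| 0 | 20 | 4.32% | 76.2% |
| 1 | 19 | 3.52% | 71.8% |
| 2 | 18 | 2.82% | 66.7% |
| 3 | 17 | 2.21% | 61.1% |
| 4 | 16 | 1.70% | 55.0% |

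For m from 15 to 20 the smallest cut-off that keeps the type I error within 5% is still 5. Excluding unscanned patients or counting them as non-responders therefore gives the same test decision. The reported rate does change: 5 responders give 5/16 = 31.3% or 5/20 = 25.0%.

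**3. What each passage supplies for an early stopper.**

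| Passage | Orders a response CT after an early stop? |
|---|---|
| 7.2.3.1 | No; requires completed treatment |
| Section 6, post-cetuximab column | Can be read so; silent on early stops and on local therapy before Week 9 |
| Section 6, surgery/RT column | No imaging |
| Footnote 5 | Nothing specific to this case |
| Section 10 | No |
| Section 13.2 | Form deadline only |

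Section 11.2 does place the post-treatment biopsy of a non-surgical patient before XRT or further systemic therapy. The CT has no equivalent rule.

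**4. A timing example.** Section 7.3.3.2 says about 90% of severe infusion reactions occur at the first infusion. A patient who stops on day 1 has best response due by day 1 + 14 = 15. Calendar Week 9 begins on day 57, 42 days later.

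**5. On-schedule patients.** Dose k falls on day 1 + 7(k−1). Dose 8 is on day 50, and day 57 opens Week 9. Section 7.2.3.1 and the schedule agree for these patients.

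**The case against.** The best reply is that the schedule already covers early stoppers. A post-cetuximab column can apply to anyone who has stopped, the surgical and radiation-oncology evaluation sits at that visit, and best response is due soon after treatment ends whether or not 8 weeks were completed. This stands in part. It rules out saying that these patients have no scan at all. It is still an inference: no passage states it, and it sets no order between the scan and local therapy.

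A reader might go further in three ways that the documents do not support.

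- **Two conflicting scan dates after a rash delay.** If held doses are made up, one delay moves a completion-based CT to day 57 + 7 = 64 or 57 + 14 = 71. Three 2-week delays move it to 57 + 42 = 99. All are outside ±2 days of day 57. The conflict disappears if Week 9 is only a nominal label for the post-cetuximab visit, or if held doses are not made up. The text does not choose, so this is an ambiguity to reconcile and not an established contradiction.
- **Section 10 ends assessment.** Only its title suggests this. Its opening sentence governs how long treatment may continue.
- **A count of affected patients from the quoted toxicity rates.** Severe rash at 1–17% gives 0.2–3.4 of 20, and severe infusion reaction at 2–5% gives 0.4–1.0. These are not stopping rates. Severe rash that improves leads to continued drug. For Grade 3–4 infusion reactions that are not serious, the narrative of 7.3.3.2 and Section 12.2 slow the infusion, while the 7.3.3.2 table stops drug at Grade 3; the sponsor must reconcile those passages. Nor does a stop always cost a scan.

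It is also fair that a patient who stops after one infusion is an unlikely responder. For such a patient the missing scan costs less power than the table shows.

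**Conclusion.** The gap is real and worth closing, though it is not fatal. The only response CT before local therapy is conditioned on completing 8 weeks, early stopping is foreseen, and no passage expressly orders the scan for those who stop. If 1 to 4 of 20 patients are unscanned, power falls from 76.2% to 71.8%–55.0%. Those figures rest on an assumed number and on missingness unrelated to response. If early stoppers respond less often than 30%, the loss of power is smaller, and leaving them out of the denominator would overstate the response rate. The sample-size calculation itself is correct. What is affected is which patients contribute to the response rate.

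**What to change.** In 7.2.3.1 and the Section 6 table:

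- Every patient who receives cetuximab has the restaging CT at the post-cetuximab visit, whether or not 8 weeks were completed.
- The visit is anchored to the end of cetuximab: the last dose given, or the decision to discontinue if that is later, with a stated window.
- In all cases the CT precedes surgery, RT or other anticancer therapy.
- Week 9 is the nominal timing for patients on schedule.

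In Section 10, state that stopping drug does not end response assessment or follow-up unless consent is withdrawn. The sponsor must also reconcile the passages on whether held doses are made up within the 8 weeks.

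A fixed calendar Week 9 for early stoppers would not work. After one 2-week delay, dose 7 falls on day 1 + 42 + 14 = 57, so the date may already have passed when the patient stops. Counting from the last dose alone also fails, because a rash stop is decided only after a hold of 1 to 2 weeks. That is why the decision date is part of the anchor.

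The cost is a few sentences and a column heading, with no extra scan for patients who complete. The downside is that the scan date varies with the actual length of treatment; it should be recorded.

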#### RECIST Criteria

Complete Response (CR)	Disappearance of all target lesions
Partial Response (PR)	At least a 30% decrease in the sum of the longest diameter (LD) of target lesions, taking as reference the baseline sum LD.
Progressive Disease (PD)	At least a 20% increase in the sum of the LD of target lesions, taking as reference the smallest sum LD recorded since the treatment started or the appearance of one or more new lesions.
Stable disease (SD)	Neither sufficient shrinkage to qualify for PR nor sufficient increase to qualify for PD, taking as reference the smallest sum LD since the treatment started.

### 7.2.4 Repeat Bx after neoadjuvant cetuximab.

After 8 weeks of neoadjuvant cetuximab, tissue will either be harvested at surgery, or if the patient is not a surgical candidate, a biopsy specimen (preferably a core biopsy as opposed to a FNA) will be procured from the primary site or accessible lymph node. As

this tissue will be used for DNA and RNA sequencing, tissue that is fresh and sufficient in quantity is required. These specimens will be flash frozen and brought that same day to the BRS.

### **7.3 Study Agent (Cetuximab)**

Cetuximab is an anti-EGFR receptor humanized chimeric monoclonal antibody. It is supplied as 100 mg/50 mL, single-use vial or a 200 mg/100 mL, single-use vial. For more information on this agent, refer to the FDA approved Package Insert.

#### **7.3.1 Dose Calculation**

Doses will be calculated on day 1 of each cycle using the patient's actual weight in the determination of body surface area. A variance of 10% of the calculated total dose will be allowed.

$BSA (m^2) = \text{square root of } ((height \text{ inches}) \times (weight \text{ lbs}) / 3131)$

#### **7.3.2 Treatment Administration**

During neoadjuvant cetuximab, the initial dose is  $400 \text{ mg/m}^2$  administered as a 120 minute intravenous infusion (maximum infusion rate 10 mg/min). The subsequent weekly doses are  $250 \text{ mg/m}^2$  infused over 60 minutes (maximum infusion rate 10 mg/min). If a weight change of  $\geq 10\%$  occurs, the cetuximab dose should be adjusted.

Cetuximab should not be delivered as an intravenous push or bolus. Administer via infusion pump or syringe pump. Do not exceed an infusion rate of 10 mg/min. Administer through a low protein binding 0.22- micrometer in-line filter. Parenteral drug products should be inspected visually for particulate matter and discoloration prior to administration, whenever solution and container permit. The solution should be clear and colorless and may contain a small amount of easily visible, white, amorphous, cetuximab particulates. Do not shake or dilute.

#### **7.3.3 Dose Modifications or Escalations**

##### **7.3.3.1 Cetuximab related Folliculitis**

Patients will concomitantly be assessed for the presence of cetuximab related folliculitis given the published correlation of folliculitis with clinical benefit (Bonner 2006). After MD visits, the patient will be assessed for the development of folliculitis characteristic of EGFR inhibition. Though the rash associated with EGFR inhibition appears similar to acne vulgaris and is commonly referred to as acne, acne-like, or acneiform, these terms are technically inaccurate. EGFR-associated rash is dominated by pustules that contain an intrafollicular collection of neutrophils—the hallmarks of an infectious folliculitis. Per Perez-Soler, the typical EGFR associated rash has a clinical presentation

characterized by pustular/popular appearance, usually involving the face, head, and upper torso, and often accompanied by pruritus, dry skin, and erythema (Perez-Soler, Zou et al. 2011).

In previous reports, the criteria used for significant EGFR associated rash has most commonly been grade 2+ on the CTCAE 4.0 criteria listed below.

CTCAE 4.0 Criteria

	1	2	3	4
Pruritus/itching	Mild or localized	Intense or widespread	Intense or widespread and interfering with ADL	—
Rash/Desquamation	Macular or papular eruption or erythema without associated symptoms	Macular or papular eruption or erythema with pruritus or other associated symptoms; localized desquamation or other lesions covering < 50% of body surface area (BSA)	Severe, generalized erythroderma or macular, papular or vesicular eruption; desquamation covering > 50% BSA	Generalized, exfoliative, ulcerative, or bullous dermatitis
Rash/Acneiform	Intervention not indicated	Intervention not indicated	Associated with pain, disfigurement, ulceration, or desquamation	—
Nail Changes	Discoloration; Ridging (koilonychias); pitting	Partial or complete loss of nail(s); pain in nail bed(s)	Interfering with ADL	—

### 7.3.3.2 Infusion Reactions

Serious infusion reactions occurred with the administration of Cetuximab in approximately 3% of patients in clinical trials, with fatal outcome reported in less than 1 in 1000. Reduce the infusion rate by 50% for NCI CTCAE Grade 1 or 2 and non-serious NCI CTCAE Grades 3–4 infusion reactions. Once the infusion rate has been decreased due to an infusion reaction, it will remain decreased for all subsequent infusions. If the subject has a second infusion reaction at the slower infusion rate, the infusion should be stopped, and the subject should receive no further cetuximab treatment. Immediately and permanently discontinue cetuximab for serious infusion reactions that are life threatening and/or require hospitalization. All patients will be premedicated with diphenhydramine hydrochloride, 50 mg, (or an equivalent antihistamine) by *i.v.* 30-60 minutes prior to the first dose of cetuximab in an effort to prevent an infusion reaction. At the discretion of the treating physician, dexamethasone, 20 mg, and an H2 blocker also may be administered.

Serious infusion reactions, requiring immediate, permanent discontinuation of cetuximab included rapid onset of airway obstruction (bronchospasm, stridor, hoarseness), hypotension, shock, loss of consciousness, myocardial infarction, and/or cardiac arrest. Severe (NCI CTCAE Grades 3 and 4) infusion reactions occurred in 2–5% of 1373 patients in clinical trials, with fatal outcome in 1 patient. Approximately 90% of severe infusion reactions occurred with the first infusion despite premedication with antihistamines.

Monitor patients for 1 hour following Cetuximab infusions in a setting with resuscitation equipment and other agents necessary to treat anaphylaxis (eg, epinephrine, corticosteroids, intravenous antihistamines, bronchodilators, and oxygen). Monitor longer to confirm resolution of the event in patients requiring treatment for infusion reactions. Immediately and permanently discontinue Cetuximab in patients with serious infusion reactions.

Infusion reactions may be managed per the following table:

Adverse Event Grade	Treatment Guidelines
Grade 1: Transient flushing or rash; drug fever < 38° C (< 100° F)	For mild infusion reactions manifesting only as delayed drug fever, consider administering prophylactic antihistamine medications for subsequent doses. Maintain the cetuximab dose, but slow the infusion rate by 50%. Acetaminophen or a non-steroidal anti-inflammatory drug (NSAID) may be administered prior to subsequent cetuximab infusions, if not otherwise contraindicated in subjects.

Grade 2: Rash; flushing; urticaria; dyspnea; drug fever $\geq 38$ C ( $\geq 100$ ° F)	For moderate infusion reactions manifesting only as delayed drug fever, slow the infusion rate for cetuximab by 50% and consider administering antihistamine medications and/or steroid medications. Maintain the cetuximab dose. Acetaminophen or a non-steroidal anti-inflammatory drug (NSAID) may be administered prior to subsequent cetuximab infusions, if not otherwise contraindicated in subjects.
Grade 3: Symptomatic bronchospasm with or without urticaria; parenteral medication(s) indicated; allergy related edema/angioedema; hypotension	Severe infusion reactions require immediate interruption of cetuximab infusion and permanent discontinuation from further treatment with cetuximab. Appropriate medical therapy including epinephrine, corticosteroids, diphenhydramine, bronchodilators, and oxygen should be available for use in the treatment of such reactions. Subjects should be carefully observed until the complete resolution of all signs and symptoms.
Grade 4: Anaphylaxis	NO FURTHER STUDY DRUG THERAPY. Life threatening infusion reactions require immediate interruption of cetuximab infusion and permanent discontinuation from further treatment with cetuximab. Appropriate medical therapy including epinephrine, corticosteroids, diphenhydramine, bronchodilators, and oxygen should be available for use in the treatment of such reactions. Subjects should be carefully observed until the complete resolution of all signs and symptoms.

**7.3.3.3 Rash:** Dermatologic toxicities, including acneiform rash, skin drying and fissuring, paronychial inflammation, infectious sequelae (for example *S. aureus* sepsis, abscess formation, cellulitis, blepharitis, conjunctivitis, keratitis, cheilitis), and hypertrichosis occurred in patients receiving Cetuximab therapy. Acneiform rash occurred in 76–88% of 1373 patients receiving Cetuximab in clinical trials. Severe acneiform rash occurred in 1–17% of patients.

Acneform rash usually developed within the first two weeks of therapy and resolved in a majority of the patients after cessation of treatment, although in nearly half, the event continued beyond 28 days. Monitor patients receiving Cetuximab for dermatologic toxicities and infectious sequelae. Instruct patients to limit sun exposure during Cetuximab therapy.

Rash occurring with Cetuximab administration may be graded according to the following table from CTCAE 4.0.

	1	2	3	4
Pruritus/itching	Mild or localized; topical intervention indicated	Intense or widespread; intermittent; skin changes from scratching (e.g., edema, papulation, excoriations, lichenification, oozing/crusts); oral intervention indicated; limiting instrumental ADL	Intense or widespread; constant; limiting self care ADL or sleep; oral corticosteroid or immunosuppressive therapy indicated	–
Purpura	Combined area of lesions covering <10% BSA	Combined area of lesions covering 10 - 30% BSA; bleeding with trauma	Combined area of lesions covering >30% spontaneous bleeding BSA;	–
Rash/acneiform	Papules and/or pustules covering <10% BSA, which may or may not be associated with symptoms of pruritus or tenderness	Papules and/or pustules covering 10 - 30% BSA, which may or may not be associated with symptoms of pruritus or tenderness; associated with psychosocial impact; limiting	Papules and/or pustules covering >30% BSA, which may or may not be associated with symptoms of pruritus or tenderness; limiting self care ADL; associated with local superinfection with oral antibiotics	Papules and/or pustules covering any % BSA, which may or may not be associated with symptoms of pruritus or tenderness and are associated

		instrumental ADL	indicated	with extensive superinfection with IV antibiotics indicated; life- threatening consequences
Rash/maculo-papular	Macules/papules covering <10% BSA with or without symptoms (e.g., pruritus, burning, tightness)	Macules/papules covering 10 - 30% BSA with or without symptoms (e.g., pruritus, burning, tightness); limiting instrumental ADL	Macules/papules covering >30% BSA with or without associated symptoms; limiting self care ADL	
Nail Discoloration	Asymptomatic; clinical or diagnostic observations only; intervention not indicated	—	—	—
Nail Loss	Asymptomatic separation of the nail bed from the nail plate or nail loss	Symptomatic separation of the nail bed from the nail plate or nail loss; limiting instrumental ADL	—	—
Nail Ridging	Asymptomatic; clinical or diagnostic observations only; intervention not indicated	—	—	—

Cetuximab dose should be modified per the following table in case of severe (grade 3/4) rash:

Occurrence of Severe (Grade3/4) acneiform	Cetuximab modification
---	------------------------

rash	
1 st Occurrence	Delay infusion 1 to 2 weeks. If there is improvement, continue cetuximab at at 250 mg/m  . If there is no improvement, discontinue cetuximab.
2 nd Occurrence	Delay infusion 1 to 2 weeks. If there is improvement, continue cetuximab at at 200 mg/m  . If there is no improvement, discontinue cetuximab.
3 rd Occurrence	Delay infusion 1 to 2 weeks. If there is improvement, continue cetuximab at at 150 mg/m  . If there is no improvement, discontinue cetuximab.
4 th Occurrence	Discontinue cetuximab

For the occurrence of grade 1 or 2 rash, see supportive care guidelines in section 7.4.5.1.

**7.3.4 Dose modifications for other toxicity:** due to lack of evidence that cetuximab contributes to these toxicities, cetuximab dose will not be altered for renal failure, fatigue, nausea/vomiting.

